#### *Low Grade Glioma Patients*

Anti-tumor activity for glioma patients will be assessed using Response Assessment in Neuro-Oncology (RANO) criteria with solid tumors through MRI. All measurable and non-measurable lesions should be assessed using the same techniques as at baseline.

Refer to Appendix 5 in the Protocol for additional information.

#### *NF-1 Associated PNs*

Response will be assessed using Dombi criteria at the time that follow-up MRI scans are performed as outlined in Section 7.1 of the Protocol.

Refer to Appendix 6 in the Protocol for additional information.

#### *LCH Patients*

Response criteria is adapted from Histiocyte Society Evaluations and Treatment Guidelines, April 2009 and is used in combination with RECIST criteria v1.1.

In the case of LCH patients, the ORR is the number of patients deemed to have treatment response (CR+REG) relative to the total number of patients treated in that cohort as described in Appendix 3 of the Protocol

Refer to Appendix 7 of the Protocol for more information.

BOR for each patient is determined from the sequence of overall responses according to the following rules for LCH subjects.

1. Complete resolution (CR)/Non-active disease (NAD) = at least two confirmed CR/NAD at least 4 weeks apart before progression
2. Regressive (REG) = at least two confirmed REG or better response at least 4 weeks apart before progression and not qualifying for a CR/NAD.
3. SD = requires at least one SD assessment or better determined at or beyond 12 weeks from randomization before progression, and not qualifying for CR/NAD or REG.
4. PD = progression after start of study treatment and not qualifying for CR/NAD or REG or SD

5. UNK = all other cases (i.e., not qualifying for confirmed CR or REG and without SD at or beyond 12 weeks or progression).

#### *All Other Solid Tumors*

Tumor response will be assessed using RECIST version 1.1 for patients with solid tumors except neuroblastomas, primary central nervous system tumors (gliomas), or PN(s).

Tumor assessments performed before the start of any further anti-cancer therapy (i.e. any additional secondary anti-cancer therapy or surgery) will be considered in the assessment of BOR. If a patient receives any further anti-neoplastic therapy while on study, any subsequent assessments will be excluded from the ORR determination.

Note that if a patient shows at least one Non-CR/Non-PD (NN) assessment determined at or beyond 12 weeks from randomization and not qualifying for CR, PR, SD, or PD, then BOR for the patient is NN.

ORR is defined as the proportion of patients with best overall response (BOR) with confirmation of CR or PR according to criteria for a specific disease type, among patients with disease assessment at baseline

BOR with confirmation and ORR will be summarized for all disease types by therapy (monotherapy or combo-therapy) and by study part and dose based on the All treated population. Where appropriate, the lesion data will be listed for each patient.

A figure of percent change at maximum reduction from baseline in tumor measurement will also be provided, where appropriate.

As sensitivity analyses, response data may also be summarized based on response-evaluable population. As supportive analyses, for LGG and NF-1 with PN patients, the response data assessed by independent review assessment will also be summarized based on the All treated population.

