### 2.7.1 Secondary endpoints

#### Overall Response Rate(ORR) by Disease Type

Overall Response Rate (ORR) is defined as the proportion of patients with best overall response (BOR) with confirmation of CR or PR according to criteria for a specific disease type, among patients with disease assessment at baseline. ORR will be calculated based on the All Treated population using investigator assessment of tumor response data and will be based on confirmed responses.

BOR for each patient is determined from the sequence of overall responses according to the following rules for RECIST 1.1, RANO, and Dombi criteria.

1. CR = at least two confirmed CR at least 4 weeks apart before progression
2. PR = at least two confirmed PR or better response at least 4 weeks apart before progression and not qualifying for a CR.
3. SD = requires at least one SD assessment or better determined at or beyond 12 weeks from randomization before progression, and not qualifying for CR or PR.
4. PD = progression after start of study treatment and not qualifying for CR or PR or SD
5. UNK = all other cases (i.e., not qualifying for confirmed CR or PR and without SD at or beyond 12 weeks or progression).

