### **2.7.3 Handling of missing values/censoring/discontinuations**

#### **Dates associated with response**

For each disease assessment after baseline, determine a date associated with the response. For complete response (CR) and partial response (PR), assign to the latest date within the disease assessments. For stable disease (SD), Non-CR/Non-PD or Not Evaluable, assign to the earliest date within the disease assessments. For progressive disease (PD), assign to the earliest assessment date associated with the progression.

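### Under the RECIST rules for residual solid tumours, Non-CR/Non-PD beyond 12 weeks followed by later progression is classed as best overall response PD, whereas the same course recorded as SD stays SD

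*SAP*

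**What the plan says.** SAP Section 2.7.1, under Overall Response Rate (ORR) by Disease Type, gives five BOR categories, "according to the following rules for RECIST 1.1, RANO, and Dombi criteria". Two matter here:

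- **SD** "requires at least one SD assessment or better determined at or beyond 12 weeks from randomization before progression", in a patient who does not reach CR or PR.
- **PD**: "PD = progression after start of study treatment and not qualifying for CR or PR or SD".

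A sixth category comes later in the same section, as a note under All Other Solid Tumors. It needs one or more Non-CR/Non-PD (NN) assessments at week 12 or later, in a patient "not qualifying for CR, PR, SD, or PD, then BOR for the patient is NN". The note does not restrict the NN assessment to the time before progression.

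Section 2.7.3 treats the two kinds of disease control as separate categories when it dates responses: "For stable disease (SD), Non-CR/Non-PD or Not Evaluable, assign to the earliest date within the disease assessments".

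BOR is reported in its own right: "BOR with confirmation and ORR will be summarized for all disease types by therapy", and also by study part and dose.

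**The concern.** BOR should record the best state a patient reached. For SD the SAP does this, since a later progression does not cancel control that was shown at or after 12 weeks. For NN it does the reverse, since a later progression removes the NN classification and leaves PD.

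NN is the code normally used when a RECIST patient has no measurable lesion. The SAP does not define it, so that is an assumption here. If it holds, two patients with the same disease course appear in different rows of the BOR table only because one had a measurable lesion. Months of control followed by progression would share the PD row with progression at the first scan.

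The classification also depends on follow-up. Treatment continues until progression or another stopping reason, and the final analysis waits until the last enrolled patient has at least 12 months on study. Each progression seen in that time turns an NN into a PD, whereas an SD already reached stays SD.

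**Working it through.** The SAP states no figure to reproduce. The check applies the rules as written to response sequences. Weeks are counted from start of treatment, because the study is not randomised and has no other starting point.

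**One patient, step by step.** NN at weeks 8, 16, 24 and 32, then progression at week 40.

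1. CR or PR: no such assessment, so not met.
2. SD: needs SD or better at or beyond 12 weeks before progression. Only NN is recorded, so not met.
3. PD: progression after start of treatment, with CR, PR and SD all not met. Met.
4. NN: requires that PD is not met. Excluded.

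BOR = PD.

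**Comparison of sequences**

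| Sequence | As written | NN counted as SD or better | NN before progression ranked above PD |
|---|---|---|---|
| NN weeks 8–32, PD week 40 | PD | SD | NN |
| SD weeks 8–32, PD week 40 | SD | SD | SD |
| NN weeks 8–32, no PD | NN | SD | NN |
| PD week 8 | PD | PD | PD |
| NN week 8, PD week 16 | PD | PD | PD |

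**All sequences.** Taking CR, NN, PD or not evaluable at each of weeks 8, 16, 24 and 32 gives 4 × 4 × 4 × 4 = 256 sequences. Between the first and third readings the only kind of change is PD to NN. Under the second reading NN is never assigned.

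**UNK rule.** It covers patients without confirmed CR or PR who have neither SD at or beyond 12 weeks nor progression. A patient with NN throughout and no progression fits that description and also fits the NN note. The note appears meant to take precedence, but the UNK rule does not say so.

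**Reach.** The note stands under a heading that covers solid tumours other than neuroblastoma, glioma and plexiform neurofibroma. LCH has its own five BOR rules, without NN. Cohorts B1, B2, B3, D1 and D2 therefore fall outside it. What remains is non-glioma V600 tumours in B4 and other RECIST tumours in Parts A and C.

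**Size per patient.** One reclassified patient moves the PD percentage by 1/10 = 10 points in a group of 10 (the planned minimum for B4) and by 1/6 = 17 points in a group of 6 (the planned size of the Part C extension). These figures show the leverage of one patient. They do not estimate how many are affected.

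**The case against.** The best defence of the text is that NN counts as SD or better, so that the patient above is classed as SD. This does not stand. Every NN at or beyond 12 weeks before progression would then be SD, the note could never apply, and Section 2.7.3 would have no reason to list the two categories separately.

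The objections on consequence are stronger, and they stand:

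- ORR counts only BOR "with confirmation of CR or PR according to criteria for a specific disease type". NN and PD are both non-responses, so ORR and its exact interval do not move. No hypothesis is tested, and the visible text defines no disease control rate.
- The path is narrow. The patient needs a residual RECIST tumour, NN at or beyond 12 weeks, no confirmed CR or PR, no SD or better at or beyond 12 weeks before progression, and progression recorded before any further anti-cancer therapy. Nothing in the SAP shows that such a patient exists.
- The note does what it was probably written to do, which is to keep patients with NN and no progression out of UNK. The missing limit to assessments before progression looks like incomplete drafting.

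Two stronger readings are tempting. A reader might infer that BOR is distorted for every disease type, because the same subsection goes on to describe summaries for all of them. The note itself sits under the RECIST heading, and none of the five disease cohorts listed in Section 2.7 (three glioma, one NF-1 with plexiform neurofibroma, one LCH) falls under it. A reader might also infer that these patients are reported as primary or early progressors. The SAP has no such category; its PD has no time limit and is not labelled that way.

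**Conclusion.** The rules are wrong as written for a small, well-defined group: RECIST 1.1 patients under All Other Solid Tumors whose disease control at or beyond 12 weeks is recorded only as NN and who progress later. They are classed as PD where the same course recorded as SD gives SD, and nothing else in the SAP corrects this.

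The consequence is limited to the PD and NN counts in descriptive BOR summaries for these tumours. ORR, its intervals and the five efficacy disease cohorts are unaffected. The number of affected patients is unknown and may be small or zero. The conclusion rests on the NN note applying only under its own heading and on NN being recorded where there is no measurable lesion. Low priority, but worth correcting before the BOR derivation is final.

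**What to change.** In SAP Section 2.7.1, for patients assessed under All Other Solid Tumors:

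- **NN**: one or more Non-CR/Non-PD assessments at week 12 or later and before progression, in a patient who does not meet CR, PR or SD.
- **PD**: extend the exceptions from CR, PR and SD to CR, PR, SD and NN.
- **UNK**: add NN to the categories that rule it out.

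Patients who progress before any NN at or beyond 12 weeks remain PD. The cost is SAP wording and one line in the BOR derivation, with no new data. PD counts may fall and NN counts rise by the same number.

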### **2.7.2 Statistical hypothesis, model, and method of analysis**

The primary analysis of response data will be performed on the All treated population by investigator assessment. Point estimate and exact confidence intervals (CIs) of ORR will be provided by disease type and by trametinib monotherapy and dabrafenib plus trametinib combination therapy, as well as by study part and dose.

### **2.7.3 Handling of missing values/censoring/discontinuations**

#### **Dates associated with response**

For each disease assessment after baseline, determine a date associated with the response. For complete response (CR) and partial response (PR), assign to the latest date within the disease assessments. For stable disease (SD), Non-CR/Non-PD or Not Evaluable, assign to the earliest date within the disease assessments. For progressive disease (PD), assign to the earliest assessment date associated with the progression.

#### **Unknown or Missing Tumor Assessments**

Patients with unknown or missing best overall response (BOR) will be counted as non-responders. If there is no baseline tumor assessment, all post-baseline overall lesion responses are expected to be 'Unknown'. If no valid post-baseline tumor assessments are available, the best overall response must be "Unknown" unless progression is reported. For the computation of ORR, these patients will be included in the All Treated Analysis Set and will be counted as 'failures'.

#### **2.7.4 Supportive analyses**

##### **ORR by independent review assessment**

The analyses of ORR will be repeated by independent review for LGG cohorts. For LGG patients, this incorporates the radiographic data which includes the lesion measurements from target lesions, non-target lesions, new lesion, corticosteroid status, and clinical status per old RANO (2010) and new RANO (2017). Please refer to the Protocol Appendix 5.

Waterfall plot will be presented for the analysis. Waterfall graphs will be used to depict the anti-tumor activity. These plots will display the best percentage change from baseline in the sum of diameters of all target lesions for each patient. Only patients with measurable disease at baseline will be included in the waterfall graphs. Patients without any valid assessments will be completely excluded from the graphs.

The total number of patients displayed in the graph will be shown. Footnote will explain the reason for excluding some patients (due to absence of any valid assessment).

##### **Concordance analysis of ORR**

Concordance analysis of ORR for LGG cohorts will be performed for assessment of the best overall responses by investigator and independent reviewer per old RANO (2010) and new RANO (2017). Concordance rate of ORR is calculated as Percent Agreement for responders and non-responders.

#### **2.8 Safety analyses**

Unless otherwise specified, all the DLT safety analyses will be based on the safety population as defined in Section 2.2 and summaries will include all events or assessments collected during the study. For all other safety analyses (i.e. AE, ECG, Labs, Vitals, etc.) they will be summarized by dose levels in Part A, by disease cohorts in Part B, by dose levels in Part C, by disease cohorts for Part D, and by five disease cohorts listed below.

- (1) Glioma Fusion subjects in Trametinib monotherapy
- (2) BRAF V600 mutant subjects in Trametinib monotherapy
- (3) BRAF V600 mutant subjects in combination therapy
- (4) NF-1 with PN subjects in Trametinib monotherapy
- (5) LCH subjects in combination therapy

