### **Safety Population**

The safety population includes all patients who received at least one dose of trametinib for Part A and Part B or at least one dose of any component of trametinib and dabrafenib combination for Part C and Part D. All safety data will be analyzed using the Safety population. In this study, the All Treated population and Safety population are identical.

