### **DLT Evaluable Population**

The DLT evaluable population is defined as those subjects participating in dose determining portion of the study (Part A and 3+3 design portion of Part A extension, Part C and Part C

extension) fulfilling the 'All Treated' population criteria and having received an adequate treatment in the first 28 days to enable an appropriate evaluation of study treatment related DLTs. Adequate exposure during the first 28 days will be defined as having received >75% of planned study treatment doses (at least 21 doses), exclusive of missed doses due to treatment-related toxicity. Any patient in the 'All Treated' population who experiences a DLT, as defined in Section 3.2.3 of protocol, will also be included in the DLT evaluable population regardless of exposure. Subjects who are either withdrawn or dose reduced due to toxicity during the first 28 days will be included in the DLT evaluable population. Patients enrolled for only PK characterization (Part A extension, Part C, or Part C extension) or for the melanoma cohort in Part C will not be observed for DLTs.

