### **Dose Limiting Toxicity**

An AE will be considered a DLT if it is considered by the investigator to be at least possibly related to study treatment, meets any of the criteria listed in Section 3.2.3.1 or Section 3.2.3.2 of protocol and occurred during the first 28 days of treatment in the dose determining portion of the study (Part A and 3+3 design portions of Part A extension, Part C and Part C extension).

DLTs will be listed and summarized for age and the dose determining portion of Part A and Part C. Only the first cycle (28 days) of treatment will be considered when summarizing data regarding the dose limiting toxicities. The table will display the number of DLT's at each dose level. AE summary of DLTs will also be presented.

Note that isolated clinical laboratory value(s) considered **not** clinically significant by the investigators are not AEs and therefore, would not be DLTs.

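### Section 2.8 assigns DLT analyses to the Safety population and leaves the DLT Evaluable Population unused, so any DLT percentage in the final report could be diluted

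*SAP*

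**What the plan says.** Three places in the SAP bear on this.

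- **Section 2.8, opening paragraph.** Unless specified otherwise, "all the DLT safety analyses will be based on the safety population as defined in Section 2.2", and the "summaries will include all events or assessments collected during the study". The Safety population is everyone with at least one dose; Section 2.2 adds: "In this study, the All Treated population and Safety population are identical".
- **Section 2.2, DLT Evaluable Population.** This set is confined to "subjects participating in dose determining portion of the study (Part A and 3+3 design portion of Part A extension, Part C and Part C" extension). It requires adequate treatment in the first 28 days, defined as "having received >75% of planned study treatment doses (at least 21 doses), exclusive of missed doses due to treatment-related toxicity". Patients who have a DLT belong to it whatever their exposure, and so do patients withdrawn or dose-reduced for toxicity in those 28 days. Patients enrolled only for PK, or "for the melanoma cohort in Part C will not be observed for DLTs". Table 2-1 gives the set its exclusion rules and Section 2.3.1 counts its members, but no analysis is assigned to it.
- **Section 2.8.1, Dose Limiting Toxicity.** DLTs are listed and summarized by age and for the dose-determining portion of Parts A and C. "Only the first cycle (28 days) of treatment will be considered when summarizing data regarding the dose limiting toxicities". The table shows the number of DLTs per dose level, and an AE summary of DLTs is also planned. No analysis population is named.

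**The concern.** A DLT-evaluable set exists so that a patient who was not treated long enough to show a DLT does not count as evidence of tolerability. The SAP defines such a set and then, in the section that governs the tables, points to a different one. Section 2.8 also admits events from the whole study, whereas Section 2.8.1 admits only the first 28 days. Two programmers following the text could produce different tables.

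At stake is how tolerability by dose reads in the final report. The primary objective is the safe and tolerable dose, and Section 2.5.2 says the Part A and Part C analyses focus on comparison between dose cohorts. If non-evaluable patients are spread unevenly over the doses, a percentage on the Safety population distorts that comparison.

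**Working it through.** **The plan's own figure.** The SAP states no DLT rate and no DLT denominator. Its only DLT figures are the escalation probabilities in Table 3-1. With true DLT rate p, and escalation on 0 of 3 or 1 of 6,

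P(escalate) = (1−p)³ + 3p(1−p)² × (1−p)³.

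| p | Table 3-1 | Recomputed |
|---|---|---|
| 10% | 0.91 | 0.906 |
| 20% | 0.71 | 0.709 |
| 30% | 0.49 | 0.494 |
| 40% | 0.31 | 0.309 |
| 50% | 0.17 | 0.172 |
| 60% | 0.08 | 0.082 |

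The table reproduces and does not depend on the population question.

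**Direction.** Let x be the patients with a DLT, e the DLT-evaluable patients and u the treated, non-evaluable patients in the same group. Section 2.2 makes every patient with a DLT evaluable, so x is the same in both sets. The percentage on the Safety population is

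x/(e+u) = (x/e) × e/(e+u).

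The factor e/(e+u) is at most 1. The percentage therefore falls or stays the same and cannot rise. The count x does not move.

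**Patients who remain in the denominator on any reading.** These are patients in the dose-determining portion who were under-exposed for reasons other than toxicity. The SAP does not say how many to expect, so u = 0 to 3 is an assumption. Take e = 6 and x = 2:

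| u | On evaluable | On Safety |
|---|---|---|
| 0 | 2/6 = 33.3% | 2/6 = 33.3% |
| 1 | 33.3% | 2/7 = 28.6% |
| 2 | 33.3% | 2/8 = 25.0% |
| 3 | 33.3% | 2/9 = 22.2% |

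**Patients who enter only on a wide reading.** Section 1.1 plans about 18 patients for Part C, including up to 6 with melanoma. With m melanoma patients among 18, and all others evaluable, the factor is (18−m)/18:

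- m = 0: 18/18 = 1.00
- m = 3: 15/18 = 0.83
- m = 6: 12/18 = 0.67

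At m = 6, four DLTs read as 4/18 = 22.2% instead of 4/12 = 33.3%, and two DLTs as 2/18 = 11.1% instead of 2/12 = 16.7%. The same reading would admit PK-only patients. The SAP does not give their number, so no figure is attached to them.

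**Whether a percentage will appear.** The one table described in the DLT text is a count. The AE summary of DLTs would carry a percentage if it follows the general AE format in Section 2.8.1, which gives number and percentage of patients. Section 2.1 takes the relevant population as denominator, and for DLTs Section 2.8 makes that the Safety population.

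**The case against.** The strongest reply is that Section 2.8 is only a default and that Section 2.8.1 overrides it. Part of this stands. Section 2.8.1 does narrow the DLT summaries to 28 days and to the dose-determining portion, which keeps out Parts B and D. It describes that portion in nearly the same words as Section 2.2, with reference to the 3+3 design. On its natural reading this also keeps out the PK-only and melanoma patients. What it does not do is name a population or apply the exposure rule, so the default denominator remains for the patients inside that portion.

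A reader might go further and infer that patients never observed for DLTs will enter the denominator and that the DLT rate is understated by a third. The SAP does not support that as a stated result. It is unclear whether the 3+3 qualifier in Section 2.8.1 applies to Part C. Section 2.2 adds a separate sentence excluding the melanoma and PK-only patients, and Section 2.8.1 has no such sentence. Their entry is therefore possible but not established. The SAP also specifies no DLT rate, so understatement depends on a percentage being shown.

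A reader might also infer that the dose decisions rest on a diluted rate. They do not. This SAP governs the final report. Section 2.11 says escalation was supported by ongoing review of safety and PK data, and Section 2.5 already refers to an established RP2D and to a dose above the MTD.

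**Conclusion.** The defect is real and limited; it should be fixed. As written, the SAP sends DLT analyses to a population that includes non-evaluable patients and leaves the set defined for the purpose unused. Its all-events clause also contradicts the 28-day limit.

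The effect is confined to percentages in the final report and can only be downward. With six evaluable patients and two DLTs, the percentage reads 33% down to 22% for zero to three under-exposed patients. That number of patients is assumed. The factor of 0.67 for Part C is the most that the melanoma patients could contribute. It needs all 6 of the permitted melanoma patients, a total of 18, and a reading of Section 2.8.1 that its wording does not clearly support. A group with no DLTs, or with every patient evaluable, would show no change.

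**What to change.** In Sections 2.8 and 2.8.1, state: *DLT summaries use the DLT Evaluable Population and the first 28 days only. They are given by dose level and by age for the dose-determining portion, that is Part A and the 3+3 portions of the Part A extension, of Part C and of the Part C extension. The number of evaluable patients is shown as the denominator.* For DLTs, delete the clause "summaries will include all events or assessments collected during the study". The Safety Population paragraph of Section 2.2 already covers the other safety analyses.

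Once this set supplies the denominator, its exposure rule should be made consistent. With one dose a day, 21 of 28 doses is 21/28 = 0.75, which does not exceed 75%, so the percentage and the dose count given in Section 2.2 do not agree.

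The cost is a few sentences in the SAP and one population flag in the DLT programs. Reported DLT percentages may come out higher than on the Safety population.
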